6.3.4.2 SRI-5 and SRI-6 Response

Like the SRI-4, the SRI-5 and SRI-6 are composite indices of SLE disease improvement that consists of scores derived from the SLEDAI-2K and the BILAG 2004 Index. However, the SRI-5 and SRI-6 are computed with a minimal three-point or five-point improvement in SLEDAI-2K being required, respectively.⁴⁶

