6.3.4 Composite Endpoints: SRI-4, SRI-5, SRI-6, and BICLA Response

6.3.4.1 SRI-4 Response

The SRI-4 is a composite index of SLE disease improvement that consists of scores derived from the SLEDAI-2K and the BILAG 2004 Index. Response based on the SRI-4 is defined by:

1) \geq 4-point reduction in SLEDAI-2K global score, 2) no new severe disease activity (BILAG A organ score) or more than 1 new moderate organ score (BILAG B), and 3) no deterioration from baseline in the PGA by \geq 0.3 points. The SRI-4 response in patients with moderate to severe SLE is associated with broad improvements in clinical and patient-reported outcomes.⁴⁵

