8.1 Sample Size

Sample size in the Phase 1b study is based on operational consideration.

The sample size in the Phase 2 study is based on the primary endpoint, SRI-4 Response at Day 210. Approximately 156 additional patients will be randomized in a 2:1 ratio to BOS161721 versus placebo to achieve 132 evaluable subjects in the FAS. This assumes 24 subjects will drop prior to having received treatment and an evaluable post-baseline efficacy measure. Enrollment and randomization will be monitored in a blinded fashion and increased if needed to ensure at least 132 subjects are randomized into the FAS.

A total of 132 subjects randomized provides more than 80% power to detect a treatment difference of 25% in SRI-4 response rates at Day 210, based on a targeted 2-sided significance level of 10% and using a 2-sided Pearson's chi-squared test. This assumes of a response rate of 65% for BOS161721 and 40% for placebo, where missing data at Day 210 is carried forward

from most recent non-missing result and subjects are treated as a non-responder if a prohibited medication defined as a medication failure occurs.

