8.2.3 Primary Efficacy Endpoint(s)

The proportion of patients who achieve a SRI-4 response at Day 210 will be assessed via Pearson's chi-squared analysis. The primary efficacy endpoint will be analyzed using the FAS and if needed repeated in the PP analysis set. Missing values will be addressed by employing a last observation carried forward (LOCF) analysis. Other imputation methods may be employed as a sensitivity analysis and will be described in the SAP. Additional analyses exploring impact of baseline factors such as baseline disease severity, race, and other characteristics may be performed.

Patients that received prohibited medications or unallowable CS usage as described in [Section 4.6](#) will be considered "medication failures" and will be treated as non-responders for the primary efficacy analysis. Patients that received an allowable CS burst but having missing data at Day 210 will considered a medication failure and will be treated as non-responders for the primary efficacy analysis. The determination of medication failures will be reviewed using blinded data and finalized prior to unblinding.

The superiority of BOS161721 relative to placebo will be evaluated. If the proportion of SRI-4 responders for the selected POC dose in BOS161721 arm is higher than that of the placebo arm, then BOS161721 will be considered superior to placebo if the 2-sided p-value is less than or

equal to 0.10. Secondary and exploratory endpoints for this POC study will be evaluated based on the same statistical hypothesis.

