8.2.4 Secondary Efficacy Endpoint(s)

Binary efficacy endpoints will be assessed via Pearson's chi-squared analysis. Continuous efficacy endpoints will be assessed via analysis of variance (ANOVA) or analysis of covariance (ANCOVA) and treatment will be compared using the F-test. Repeated measures mixed models may be performed to evaluate data collected at each visit and overall. Time-to-event endpoints will be assessed via Kaplan-Meier methodology and treatment will be compared using the log-rank test. The secondary efficacy endpoints will be analyzed on the FAS and if needed repeated in the PP analysis set. Details including handling of missing data and "medication failures" will be available in the SAP.

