
 • CCI [REDACTED] 	
 • CCI [REDACTED] • CCI [REDACTED] 	
The rules for CS usage during the trial, as well as limitations of other prohibited medications, are applied on the analytical end to ensure SRI-4 responders meet all necessary criteria.

Section	Description of Changes	Rationale
		
CCI
 
[Redacted]

 CCI [Redacted] 		
 CCI [Redacted]

 CCI [Redacted] 		
 CCI [Redacted]

POC Phase 2 Study

OBJECTIVES	ENDPOINTS
Primary	

 To demonstrate a superior effect of BOS161721 at the chosen dose compared with placebo for response on the SLE Responder Index 4 (SRI-4) 	
Primary Efficacy Endpoint
 
 The proportion of subjects with a SRI-4 response at Day 210 (see Section 6.3.4.1)
Secondary	

Section	Description of Changes	Rationale
	
To demonstrate a superior effect of BOS161721 at the chosen dose compared with placebo for response on clinical indicators of SLE activity, in adult patients with moderately to severely active SLE on limited background standard of care treatment
	
Secondary Efficacy Endpoints
 
 • The proportion of subjects with: 
 - SRI-4 response at each visit - SRI-5 and SRI-6 response (Section 6.3.4.2) - a sustained reduction of oral corticosteroid (CS) (≤ 10 mg/day and \leq Day 0 dose) between Day 120 and Day 210 - new BILAG A flare or > 1 BILAG B flares relative to baseline through Day 210 - PGA worsening - a BICLA response - a CLASI response - medication failures • Results and changes from baseline in: 
 - CLASI - swollen and tender joints ACR-28 - SLEDAI-2K - SLICC/ACR damage index • Time to medication failure • Duration of SRI-4 response • Time to first SRI-4 response • Time to BILAG A flare or > 1 BILAG B flare compared to baseline through Day 210

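### The SRI-5 and SRI-6 thresholds are written as 3 and 5 points, so SRI-5 is easier to meet than SRI-4 and neither endpoint measures what its name says

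*Protocol*

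**What the plan says.** Section 6.3.4.1 gives SRI-4 three components. The first is a SLEDAI-2K reduction of at least four points ("4-point reduction in SLEDAI-2K global score"). The second bars any new BILAG A score and more than one new BILAG B score. The third bars a PGA deterioration of 0.3 points or more.

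Section 6.3.4.2 then states: "Like the SRI-4, the SRI-5 and SRI-6 are composite indices of SLE disease improvement". The only difference it names is the SLEDAI-2K requirement: "the SRI-5 and SRI-6 are computed with a minimal three-point or five-point improvement in SLEDAI-2K being required, respectively".

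The Phase 2 endpoint list, as reproduced in Appendix 7, makes these secondary efficacy endpoints and points to this section for their definition: "SRI-5 and SRI-6 response (Section 6.3.4.2"). Section 8.2.4 sets the test: "Binary efficacy endpoints will be assessed via Pearson's chi-squared analysis". Section 8.2.3 sets the criterion: "Secondary and exploratory endpoints for this POC study will be evaluated based on the same statistical hypothesis". For the primary endpoint that means superiority if the active rate is higher and the two-sided p-value is at most 0.10.

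**The concern.** SRI-4 is a reduction of at least 4 points, so a reader takes the index number to be the required reduction. On that reading SRI-5 and SRI-6 are successively harder versions of the primary endpoint. The written thresholds break this in two ways. SRI-5, at 3 points, falls below SRI-4. SRI-6, at 5 points, carries the threshold that belongs to SRI-5.

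Both endpoints receive formal tests, so the written rule decides what is reported. A programmer who follows Section 6.3.4.2 would report a 3-point response as SRI-5 and a 5-point response as SRI-6. One who follows the index names would depart from the protocol. If the conflict were noticed only after unblinding, the thresholds would be chosen with the results in view.

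**Working it through.** **1. The plan's own figure.** The only power statement concerns SRI-4 (Section 8.1): 132 patients randomized 2:1, a "response rate of 65% for BOS161721 and 40% for placebo", a "targeted 2-sided significance level of 10" percent, and power above 80%.

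- Arms: 132 × 1/3 = 44 placebo and 132 × 2/3 = 88 active.
- Pooled rate: (88 × 0.65 + 44 × 0.40)/132 = 74.8/132 = 0.567.
- Standard error under no difference: √[0.567 × 0.433 × (1/44 + 1/88)] = 0.0915.
- Standard error under the alternative: √[0.40 × 0.60/44 + 0.65 × 0.35/88] = 0.0897.
- Power: Φ[(0.25 − 1.645 × 0.0915)/0.0897] = Φ(1.11) = 0.866. Exact enumeration of the Pearson chi-squared test gives 0.863.

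The stated figure reproduces. It uses SRI-4 only, so it does not depend on the SRI-5 or SRI-6 thresholds.

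**2. Classification by SLEDAI-2K reduction.** Assume the BILAG and PGA components are met. Written thresholds are SRI-4 at least 4, SRI-5 at least 3 and SRI-6 at least 5. The index names imply SRI-5 at least 5 and SRI-6 at least 6.

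| Reduction (points) | SRI-4 | SRI-5 as written | SRI-6 as written | SRI-5 by name | SRI-6 by name |
|---|---|---|---|---|---|
| 2 | no | no | no | no | no |
| 3 | no | **yes** | no | no | no |
| 4 | yes | **yes** | no | no | no |
| 5 | yes | yes | **yes** | yes | no |
| 6 | yes | yes | yes | yes | yes |

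Bold cells are those where the written rule and the name disagree. The written order of strictness is SRI-5 (3) < SRI-4 (4) < SRI-6 (5), where the names imply 4 < 5 < 6. The written SRI-6 column is identical to the SRI-5-by-name column.

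**3. Effect on the rates.** Let f3, f4 and f5 be the proportions of an arm who fall by exactly 3, 4 or 5 points and meet the other components.

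- Written SRI-5 rate = SRI-4 rate + f3, so it can never be below the SRI-4 rate.
- Written SRI-5 rate − SRI-5 rate by name = f3 + f4.
- Written SRI-6 rate − SRI-6 rate by name = f5.

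The protocol does not give f3, f4 or f5. At the planning rates of 65% and 40%, f3 can lie anywhere from 0 to 35% on active and from 0 to 60% on placebo. The written SRI-5 rate would then lie between 65% and 100% on active and between 40% and 100% on placebo. If f3 is zero in both arms, the written SRI-5 simply repeats the primary endpoint.

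**4. Can another reading rescue the sentence?** Reading the minimum as strictly more than five points would give SRI-6 at least 6. The same reading makes SRI-5 more than three, that is at least 4, which is SRI-4 again. No single reading gives 5 and 6. No other part of the document shown gives different thresholds. The two earlier protocol versions reproduced after Appendix 7 carry the same sentence in their Section 7.3.4.2, so no amendment corrected it.

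**The case against.** The strongest counter-argument is about weight. The primary endpoint, sample size and power rest on SRI-4. SRI-5 and SRI-6 are two of many secondary endpoints in a proof-of-concept study, and the text shown gives them no power statement and no gatekeeping role. SLEDAI-2K is recorded as a score and its change is itself a secondary endpoint, so any threshold can be derived later. All of this stands and limits the damage to these two endpoints. It also means the error can be fully repaired before unblinding.

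The protocol nowhere states that the index number is the threshold; that is inferred from SRI-4. The source cited for the SRI-5 and SRI-6 thresholds was not available. This too stands: 5 and 6 as replacements are inferred from the protocol's own naming. The contradiction needs no outside source, because SRI-5 at 3 points sits below SRI-4 at 4 in adjoining sections.

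The nesting of SRI-4 within the written SRI-5 requires the same BILAG and PGA rules, and Section 6.3.4.2 does not restate the PGA rule. Dropping PGA would loosen SRI-5 further, so the ordering survives.

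Finally, SRI-6 as written is still stricter than SRI-4. That is correct: only SRI-5 is inverted, and SRI-6 is one point short of its name.

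Leaving the matter to the SAP does not help. The protocol states a definition here, and an SAP using 5 and 6 points would contradict it.

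**Conclusion.** The definition is wrong as written and must be corrected. SRI-5 is easier to meet than SRI-4: a fall of exactly 3 points fails SRI-4 but counts for SRI-5. SRI-6 accepts a 5-point fall under a 6-point name. The SRI-5 rate is overstated by f3 + f4 and the SRI-6 rate by f5, relative to what the names imply. The size of these shifts, and their effect on the treatment comparison, cannot be determined from the protocol.

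This rests on three assumptions: the index number denotes the minimum reduction, as it does for SRI-4; the BILAG component is the same across the three indices, and the PGA component is either the same or absent; and missing data and medication failures are handled alike for all three.

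**What to change.** Replace the threshold sentence in Section 6.3.4.2 with: *SRI-5 and SRI-6 require a reduction of at least 5 and at least 6 points in SLEDAI-2K, respectively; the BILAG and PGA components are as for SRI-4.* Check the SAP and the endpoint programming against the same thresholds, and settle this before unblinding. The responder sets are then nested, with SRI-6 inside SRI-5 inside SRI-4.

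Visits, data collection, sample size and power do not change. Section 11 requires a permanent change to go through an amendment with IRB/IEC approval, so the cost is low but not nil. The sentence can travel with the next amendment if that comes before unblinding.

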6.3.4.3 BICLA Response

The BICLA is a responder index developed to measure response to therapy, and it includes scores from the BILAG, SLEDAI-2K, and PGA. BICLA response is defined as 1) at least 1 gradation of improvement in baseline BILAG 2004 scores in all body systems with moderate disease activity at entry (eg, all B [moderate disease] scores falling to C [mild], or D [no activity]); 2) no new BILAG A or more than 1 new BILAG B scores; 3) no worsening of total SLEDAI-2K score from baseline; 4) \leq 10% deterioration in PGA score and 5) no treatment failure.⁴⁴ It is driven primarily by the BILAG, and has been used in Phase 2 and 3 mAb studies.⁴⁷

For the endpoints of BICLA response at Days 210, 240, and 270, patient scores will be completed and response determined.

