6.3.2 BILAG 2004

The BILAG-2004 index is an organ-specific 97-question assessment based on the principle of the doctor's intent to treat. Only clinical features attributable to SLE disease activity are to be recorded and based on the patient's condition in the last 4 weeks compared with the previous 4 weeks. It will be scored as not present (0), improved (1), the same (2), worse (3), or new (4). Disease activity is graded separately for 9 body systems to 5 different grades (A to E) as follows: A ("Active") is very active disease, B ("Beware") is moderate activity, C ("Contentment") is mild stable disease, D ("Discount") is inactive now but previously active, and E ("Excluded") indicates the organ was never involved.⁴⁴ A shift from BILAG-2004 Grade A or B to a lower grade indicates a clinically relevant change in disease activity as the BILAG-2004 grades mirror the decision points for treatment interventions.

Only investigators that complete BILAG-2004 training will be allowed to perform the BILAG-2004 assessments. Preferably, the same investigator should evaluate the patient at each BILAG-2004 assessment from screening to study completion. The investigator must maintain documentation with descriptive details supporting the BILAG-2004 scoring (eg, chart, worksheet, clinic notes, and labs) at each visit.

See [APPENDIX 5](#) for detailed specifications.

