Section	Description of Changes	Rationale
	systems for a total of 2 “B” BILAG body system scores	
	With:	
7	Patients must have at least 1A or 2Bs from the following manifestations of SLE, as defined by the BILAG criteria as modified for use in this study, which must be confirmed by the central data reviewer:	
	a BILAG A or B score in the mucocutaneous body system	
	b BILAG A or B score in the musculoskeletal body system due to active polyarthritis defined as follows:	
	i “BILAG A:” Severe Arthritis, (BILAG item number 41), manifested by observed active synovitis in ≥ 2 joints with marked loss of functional range of movements and significant impairment of basic activities of daily living that has been present on several days cumulatively over the past 30 days , including at the time of the screening visit. See APPENDIX 5 for additional detailed specifications.	
	• Basic ADLs are defined as the following activities which require assistance or assistive devices, (at least 1 must be present and documented in source):	
	○ Ambulation, toileting, grooming- including bathing and dressing; feeding oneself	
	ii “BILAG B:” Moderate Arthritis, Tendonitis or Tenosynovitis, (BILAG item number 42), defined as tendonitis/tenosynovitis, or active synovitis in ≥ 1 joint, (observed or throughout history), with some loss of functional range of movements which lead to some loss of functional range of motion as manifested by effects on instrumental ADLs such as:	
	• Cooking, driving, using the telephone or computer, shopping, cleaning, etc, and has been present on several days over the last 30 days , and is present at the time of the screening visit	
	If only one “B” and no “A” score is present in the mucocutaneous body system or in the musculoskeletal body system due to arthritis, then at least 1 “B” must be present in the other body systems for a total of 2 “B” BILAG body system scores	

Section	Description of Changes	Rationale
Section 5.1, Screening	Add: 
Direct Coomb's test (if indicated for hemolytic anemia)	Text updated to clarity
Section 5.2, Enrollment/Randomization and Day 0 Treatment		
Section 5.3, Treatment Period/Follow-Up Visits		
Section 5.4, Safety Follow-Up Visits		
Section 5.1, Screening	Delete: 
CD4+ count, total IgG and IgM levels, plasma CCI, plasma CCI and CCI whole blood for leukocyte immunophenotype; CCI	Updated to clarify the planned laboratory assessments

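### BICLA criterion 1 asks for improvement only in BILAG B systems, so a patient who enters with a BILAG A and stays at A can count as a responder

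*Protocol*

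**What the plan says.** Section 6.3.4.3 gives BICLA response five parts. The first is "at least 1 gradation of improvement in baseline BILAG 2004 scores in all body systems with moderate disease activity at entry", and its only example is "all B [moderate disease] scores falling to C [mild], or D [no activity". The second is "no new BILAG A or more than 1 new BILAG B scores". The third is "no worsening of total SLEDAI-2K score from baseline". The fourth limits PGA deterioration to 10%, and the fifth is absence of treatment failure.

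The grades are explained in Section 6.3.2, where A is very active disease and B is moderate activity. The SRI-4 definition in Section 6.3.4.1 uses the same scale, calling an A organ score severe and a B organ score moderate. Section 6.3.2 also states: "A shift from BILAG-2004 Grade A or B to a lower grade indicates a clinically relevant change in disease activity".

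On entry, the replacement text for inclusion criterion 7 in Appendix 7 (entry for Section 4.4) reads: "Patients must have at least 1A or 2Bs from the following manifestations of SLE". It asks for a second B only when no A is present.

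On analysis, Section 8.2.4 assesses binary secondary endpoints by Pearson's chi-squared test. Section 8.2.3 applies the same hypothesis to secondary endpoints as to the primary, at two-sided 0.10.

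**The concern.** On the protocol's own vocabulary, moderate means B and does not include A. Criterion 1 therefore never asks a baseline A to improve, and criterion 2 bars only a new A. The rule is looser for the graver entry state than for the milder one. This is at odds with Section 6.3.2, which treats a drop from either A or B as the clinically relevant change.

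Patients whose worst organ system has not moved could be counted as treatment successes in both arms. That raises both response rates. Where stability without improvement is about as common on placebo as on active drug, it also narrows the difference that the test is meant to detect.

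**Working it through.** **Logic check.** The five criteria were applied as written to six baseline-to-follow-up BILAG profiles, with SLEDAI-2K and PGA unchanged and no treatment failure. They were then reapplied with criterion 1 extended to systems graded A or B. A baseline A that falls to B was not counted as a new B. Counting it would change nothing here, since one new B is allowed.

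| Baseline to follow-up | As written | A or B must improve |
|---|---|---|
| A to A | responder | non-responder |
| A to B | responder | responder |
| B, B to B, B | non-responder | non-responder |
| B, B to C, C | responder | responder |
| A, B to A, C | responder | non-responder |
| A, B to A, B | non-responder | non-responder |

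The first row passes because criterion 1 is empty (no B at entry), the A is not new, and nothing else has worsened. Only the first and fifth rows change under the extended criterion; these are the two in which a baseline A persists while the patient is called a responder.

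**Size, as illustration only.** The protocol states no BICLA rate or power, so there is no BICLA figure to reproduce. Section 8.1 gives 132 patients at 2:1, hence 88:44, and a two-sided level of 0.10. The formula is power = Φ[(|p1 − p0| − 1.645·s0)/s1], where s0 uses the pooled rate and s1 the separate rates. For the primary endpoint (65% vs 40%) it gives 86.6%, in line with the stated figure of more than 80%.

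The following inputs are assumptions, not taken from the documents: true BICLA rates of 50% and 30%; a share f of each arm entering with A only; and a share s of those patients who merely do not worsen. The observed rates become 0.50(1 − f) + f·s on active and 0.30(1 − f) + f·s on placebo.

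- f = 0: 50% vs 30%, s0 = 0.0915, s1 = 0.0873. (0.20 − 0.1505)/0.0873 = 0.567, power 71.5%.
- f = 0.20, s = 75% in both arms: 55% vs 39%, s0 = 0.0923, s1 = 0.0907. (0.16 − 0.1518)/0.0907 = 0.09, power 53.6%. Any common s from 65% to 85% gives about 54%.
- f = 0.20, s = 85% active and 75% placebo: 57% vs 39%, power 62.2%.
- f = 0.20, s = 85% active and 65% placebo: 57% vs 37%, power 70.4%.
- With equal s, power is about 67% at f = 0.05, 62-63% at f = 0.10 and 45% at f = 0.30.

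The sketch covers A-only patients and leaves out those with A and B. The result turns mainly on f and on how s differs between arms, and the documents give neither.

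**The case against.** The sentence may be shorthand. BICLA is introduced as an existing index with a citation, the B example is offered as an example, and Section 6.3.2 values a shift from A or from B. Loose wording is more likely than a deliberate decision that an A need not improve. That is a fair reading of intent, but the example illustrates moderate activity, which the protocol ties to B, so it does not widen the criterion. Section 8.2.4 leaves details of the secondary analyses to the SAP. Here, though, the protocol states a complete rule, and an SAP would have to repeat it or contradict it.

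Some text is also unseen. Treatment failure, the fifth criterion, is not defined in the part available; a definition that included a persisting A would close the gap. The nearest rule, medication failure in Section 8.2.3, concerns prohibited medication, steroid use and missing data after a steroid burst. The current Section 4.4 is likewise not in the part available. Entry on a single A rests on the replacement text in Appendix 7, and the superseded criterion admits it too. The study-specific BILAG criteria in Appendix 5 are redacted. These points leave some uncertainty, but nothing shown removes the defect.

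The objection carries most weight on consequence. BICLA response is one of many secondary endpoints. The primary is SRI-4, which requires a fall of at least 4 points in SLEDAI-2K and does not use this criterion. Patients entering on two Bs with no A are scored as intended.

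**Conclusion.** The point holds as a defect in a stated rule. As written, an unchanged A can be scored as a BICLA response, and so can an A with B whose B alone improves, while two unchanged Bs cannot. This misclassifies the more severely affected patients on a formally tested secondary endpoint. It should be fixed, but it does not threaten the trial's main conclusion: the SRI-4 endpoint and its sample size are untouched.

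A reader might infer that the BICLA result becomes uninterpretable, or that power drops from about 71% to 54%. The documents support neither. The share of patients entering with A and no B is not given, so the extent of misclassification is unknown. The 54% figure needs both a 20% A-only share and equal non-worsening in the two arms; if non-worsening is 10 to 20 points higher on active drug, power is about 62% to 70%. The assumed 50% and 30% rates are not the protocol's either.

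The conclusion rests on reading moderate as B, on entry with a single A being allowed, and on treatment failure not being defined elsewhere to include a persisting A.

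**What to change.** Rewrite criterion 1 in Section 6.3.4.3 so that every body system graded A or B at baseline must improve by at least one grade: A to B, C or D, and B to C or D. Leave criteria 2 to 5 as they are. Carry the same wording into the SAP derivation and settle it before unblinding.

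The cost is one sentence in the protocol and one line in the derivation. The BILAG grades are already collected at every efficacy visit, so no new data are needed.
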